1.2 Purpose

This Phase II/III study aims to evaluate PK, safety, tolerability and efficacy of a new formulation of artemether-lumefantrine dispersible tablet in infants and neonates <5 kg body weight with acute uncomplicated *Plasmodium falciparum* malaria.

2 Objectives and endpoints

Table 2-1 Objectives and related endpoints

| Objective(s) | Endpoint(s) |
|---|--|
| Primary objective(s) | Endpoint(s) for primary objective(s) |
| 
To assess the key PK parameter of artemether in infants and neonates < 5 kg body weight dosed with the new formulation of artemether-lumefantrine dispersible tablet | 
Artemether C_{max} (represents the higher concentration between the concentrations at 1 hour and 2 hours after first dose) |
| Secondary objective(s) | Endpoint(s) for secondary objective(s) |
| 
To assess other key PK parameters of artemether, DHA and lumefantrine in infants and neonates <5 kg body weight dosed with the new formulation of artemether-lumefantrine dispersible tabletTo evaluate the safety and tolerability of the new formulation of artemether-lumefantrine dispersible tablet in infants and neonates <5 kg body weight with acute uncomplicated P. falciparum malariaTo determine the efficacy of the new formulation of artemether-lumefantrine dispersible tablet for treatment of acute uncomplicated P. falciparum malaria in infants and neonates <5 kg body weight | 
Lumefantrine Day 8 concentration (C_{168h}) Artemether AUC, DHA and Lumefantrine C_{max} and AUC as appropriateSerious adverse events (SAEs), adverse events (AEs), and routine safety laboratory assessmentsPCR-corrected Adequate Clinical and parasitological Response (ACPR) at Days 15, 29, and 43 Uncorrected ACPR at Days 8, 15, 29, and 43 |

| Objective(s) | Endpoint(s) |
|--------------|--|
| | Incidence rate of recrudescence and new infections at Days 15, 29 and 43 Parasite and Fever clearance Times (PCT and FCT) |
| | |

3 Study design

This will be a multicenter, open-label, single-arm, adaptive design with dose adaptation (de-escalation or escalation) study in infants and neonates <5 kg body weight with *P. falciparum* malaria.

A total of approximately 44 male and female infant/neonate patients (<5 kg) are planned to be recruited in the study. There will be two sequential and age-descending cohorts of approximately 22 patients each (see [Figure 3-2](#)), all <5 kg: Cohort 1 of infants >28 days of age, and Cohort 2 of neonates ≤ 28 days of age. Cohort 2 will include 3 age subgroups (15-28, 8-14 and 1-7 days), starting with the highest age subgroup in Cohort 2.1. The two lower age subgroups (i.e., 8-14 and 1-7 days) will be recruited in parallel. These two subgroups will be optional, depending on recruitment feasibility.

In the event of inadequate exposure ([Section 4.2](#)), determined at predefined PK checkpoints (i.e., after the first 9 patients in Cohort 1, and after the first 3 patients and then the first 9 patients of Cohort 2 (1-28 days of age)), additional patients may be recruited up to a total of 98 patients across the 2 cohorts ([Figure 3-2](#)). An additional PK check may be performed after the first 9 patients of the 15-28 days age group in Cohort 2 have been recruited. For Cohort 2, if an adequate dose cannot be determined or if recruitment is not feasible in any age subgroup, the cohort may be closed and 22 additional patients may be recruited in Cohort 1 up to a total of approximately 44 patients treated with the same dose (instead of the planned 22 patients). Cohort 2.3 will start recruitment after the dose used in Cohort 2.2 has been assessed to be appropriate.

[figure not shown]
Patients will be admitted to the hospital on or before Day 1 (see [Figure 3-1](#)). After meeting all the inclusion and exclusion criteria in the study, they will receive study drug. The starting dose regimen in Cohort 1 will be two dispersible tablets twice daily for three consecutive days. The

dose must be preceded and/or followed as much as possible by food/drinks rich in fat, e.g. breast milk, or formula milk.

Patients will remain in the hospital under close supervision until they are discharged by the investigator or designee on Day 4. At the discretion of the investigator, patients may stay for a few additional days if needed. The patients will be then followed up at regular intervals until Day 43 (core follow-up), in order to assess study drug exposure, safety, tolerability and efficacy (See Visit schedule in [Table 8-1](#)). If symptoms re-emerge outside the scheduled study visits, parents/legal guardians of the patients will be instructed to contact the investigator. In case of treatment failure (as per WHO definition), rescue treatment according to local clinical practice will be provided.

[figure not shown]
Patients will then attend a long term safety follow-up visit

Figure 3-1 Patient participation overview

In this study, a stepwise and sequential approach will be adopted in order to minimize the risk for patients ([Figure 3-2](#)).

Figure 3-2 Study flow chart

PK exposure checks (together with safety and efficacy data review as available) will be performed on a periodic basis to assess the dose included at the following timepoints:

- 1) once the first 9 patients in Cohort 1 have been dosed and followed up to Day 15,
- 2) once the first 3 patients in Cohort 2 (15-28 days age subgroup) have been dosed and followed up to Day 15,
- 3) once the first 9 patients in Cohort 2 (1-28 days age subgroup) have been dosed and followed up to Day 15. In case exposure data in the 9 patients from the 1-28 day subgroup are not sufficient to make a decision on dose selection (e.g., due to a significantly different exposure across age subgroups), as many additional patients as needed to reach a total of 9 (across Cohort 2.1 and 2.2) in the 15-28 day subgroup specifically will be recruited in Cohort 2.2 and treated with the same dose. An additional PK check will then be performed after these additional patients will have been followed up to Day 15.

A total of 9 patients in a defined age group should allow to confirm with reasonable confidence if ART C_{max} is within approximately 2-fold (safety interval) of the C_{max} which has been found to be safe and efficacious in previous studies; a total of 3 patients will however allow to check at an early stage if the ART C_{max} range is within the expected safety interval (Cohort 2 only).

An Independent Data Monitoring Committee (DMC) will review the PK, efficacy and safety data at these checks, and also at two planned interim data assessments, one between the two cohorts, and another one after all patients in Cohort 2 have completed Day 43 (Figure 3-2).

The interim data assessment based on Cohort 1 data will serve to determine the starting dose level for Cohort 2 (for further details see [Section 10.2.1](#)).

Based on these checks, the dose being considered will be assessed as suitable or not for the subgroup of patients treated.

In Cohort 1:

- if the dose is deemed adequate in the first 9 patients (based on PK, safety and efficacy data review as available), additional patients will be recruited up to approximately 22 treated with the same dose level (expansion phase).
- if the dose is not adequate, the first set of 9 patients will be repeated, up to twice, using a different dose level, until a dose level is determined as suitable.

In Cohort 2:

- if the dose is deemed adequate in the 3 patients from the highest age subgroup (15-28 days), recruitment of 6 additional patients in the 1-28 day subgroup will be attempted.
- if the dose is not adequate, the first set of 3 patients from the highest age subgroup (15-28 days) will be repeated, up to twice, using a different dose level, until a dose level is determined as suitable. Then, recruitment of 6 additional patients in the 1-28 day subgroup will be attempted.
- Another PK check (together with safety and efficacy data as available) will then be performed when a total of 9 patients have been treated with the same suitable dose in the 1-28 day subgroup. In case exposure data from these 9 patients (1-28 day subgroup) is not sufficient to make a decision on dose selection, as many additional patients as needed to reach a total of 9 (across Cohort 2.1 and 2.2) in the 15-28 day subgroup specifically will be recruited in Cohort 2.2 and treated with the same dose. An additional PK check will then be performed after these additional patients will have been followed up to Day 15. If the former PK check shows that the dose is suitable for all subgroups, expansion of Cohort 2 will include all age subgroups. If it is unsuitable for any of the two lower age subgroups, no further patients will be recruited in this/these lower age subgroup(s), and further expansion of Cohort 2 will only include patients from the 15-28 day subgroup. In the case the dose is not confirmed as suitable for the highest age subgroup, a repeat run with 9 patients (3+6 patients) will be performed using a different dose.

In Cohort 2, if through the steps above, no suitable dose has been determined in the higher age subgroup (15-28 days), recruitment will be stopped in that cohort and an additional 22 patients will instead be recruited in Cohort 1 and treated with the dose that was deemed adequate in that cohort.

Once either cohort's expansion has been completed with approximately 22 patients treated with the same, suitable dose, or any of the alternative scenarios described above, patients will be followed up to Day 43, when the complete set of key efficacy and safety parameters and PK exposures will be assessed.

Note: Patients treated with dose levels deemed not suitable will also be closely followed up to Day 43 and at one year of age.

In the unlikely case when all the iterations described above would have to be implemented, a maximum of 98 patients would be recruited.

4 Rationale

4.1 Rationale for study design

This will be a multicenter, open-label, single-arm, adaptive dosing study in infants and neonates <5 kg body weight with acute uncomplicated *P. falciparum* malaria.

The objective of this Phase II/III study design is to test the new artemether-lumefantrine dispersible tablet formulation to determine exposure to artemether, DHA and lumefantrine as well as its safety, tolerability and efficacy in patients <5 kg with uncomplicated *P. falciparum* malaria.

The open-label, adaptive, sequential-group design used in the study aims to minimize the risk by studying first a cohort of infants (>28 days of age, <5 kg) that is similar to the population already evaluated in previous clinical trials (i.e., infants ≥5 kg body weight, irrespective of age). The risk of bias arising from an open-label design is minimized as objective endpoints have been chosen for the study.

Patients will be enrolled at sites experienced in managing the population targeted in the present study (neonates and infants <5 kg BW) and they will be hospitalized during the treatment period in order to ensure close monitoring.

The planned periodic pharmacokinetic exposure check after dosing a limited number of patients (as specified in Section 3 of this protocol), along with the review of the available efficacy and safety data by the DMC, aims to minimize the risk for patients, and it will also allow to adjust the dose in case of inadequate outcome.

The design of the core follow-up (up to Day 43) within each cohort is well established for malaria trials and follows WHO guidelines.

Since central nervous system (CNS) toxicity with artemisinin derivatives has been reported in animal studies, the neurological safety of artemether-lumefantrine has been a subject of much attention ([Adjei et al 2009](#)). However, CNS toxicity has not been reported in well designed clinical trials ([Chattopadhyay et al 2007](#)), including ototoxicity ([Carrasquilla et al 2012](#)), nor in the previous clinical study (COA566B2306 in infants >28 days and <5 kg) with a similar design to the current study's ([Tiono et al 2015](#)).

4.2 Rationale for dose/regimen and duration of treatment

Dose selection in this study is based on extensive safety and efficacy experience with artemether:lumefantrine 20 mg:120 mg and also specifically based on data from the controlled clinical trial in infants and children ≥5 kg BW, study B2303 (COA566B2303) as well as on the results of a previous study, study B2306 (COA566B2306) in this very young population (infants < 5 kg BW and > 28 days) (See [Table 4-1](#)).

In Study B2306, exposure to artemether and DHA was around 2-3 fold higher in 20 infants <5 kg BW and >28 days compared to infants ≥5 kg BW, irrespective of age (Study B2303), whereas the exposure to lumefantrine was comparable between these two studies ([Tiono et al 2015](#)). The dose regimen administered to infants <5 kg body weight (study B2306) and to those

5-<15 kg BW (study B2303) was the same (a 6-dose regimen of artemether:lumefantrine 20 mg:120 mg of over 3 days). The higher artemether exposure at a lower age and weight could result from immature metabolic enzymes mainly CYP3A4 and CYP2B6 ([Lin et al 2016](#)). The safety profile associated with a higher systemic artemether exposure, could not be fully supported by preclinical data:

- in dogs, pathological evidence of neurotoxicity was noted with intramuscular doses of artemether administered daily for 8 days.
- monkeys were less susceptible to artemether-induced neurotoxicity ([Li and Hickman 2011](#)).

Although difficult to interpret, available clinical data do not suggest that artemether C_{max} values exceeding those associated with neurotoxicity in dogs have resulted in neurological effects in infants. Given the highly vulnerable patient population in this study, it is nevertheless imperative to bring the exposure of artemether within the limits which have been clinically proven to be safe (See [Table 4-1](#) below).

On the other hand, lumefantrine exposure was generally comparable between Study B2306 and Study B2303 except for the Day 8 exposure which was more than 2-fold higher in Study B2306. A potential reason for this observation was a reduced intestinal absorption combined with reduced clearance in patients <5 kg BW leading to a comparable exposure during the dosing period between the two groups of infants /children.

Table 4-1 Historical exposure values from previous studies

| Study | Body weight (age) | ART Dose (mg) | n | First dose Artemether C_{max} (ng/mL) | LUM C_{max} (μ g/mL) | LUM $C_{168\ h}$ (ng/mL) |
|-------|-------------------|---------------|----|---|-----------------------------|--------------------------|
| B2306 | <5kg >28days | 20 | 18 | 509 ± 309 | 6.38 | 815 |
| B2303 | ≥5 - <15 | 20 | 55 | 196 ± 204 | 5.16 | 386 |
| B2303 | ≥15 - <25 | 40 | 29 | 150± 106 | 8.03 | |
| B2303 | ≥25 - <35 | 60 | 8 | 134 ± 56.7 | 12.3 | |

ART: artemether; LUM: lumefantrine

Based on the above data and on ontogeny data (course of development of the human organism), a full PBPK model was developed and validated. This model was used to simulate exposures to artemether and lumefantrine corresponding to different doses and at different neonate and infant ages (Report DMPK R1809279) (See [Table 4-2](#) below).

While selecting the doses for the present study, the following considerations were taken into account:

- due to artemether's potential neurotoxicity (based on animal data), it is hypothesized that its exposure should be contained within the range that has been found to be well tolerated and efficacious in children ≥ 5 kg.
- Exposure to lumefantrine should also be adequate, especially the Day 8 plasma concentration (which is a surrogate efficacy marker), i.e., it should be ≥ 200 ng/mL on

Day 8 based on an extensive meta-analysis, ([WWARN 2015](#)) to achieve long-term parasite clearance.

- within the exposures which were found to be well tolerated in children ≥ 5 kg BW, while kept on the higher side, due to lower immunity and potential lower exposure in pediatric patients ([Kloprogge et al 2018, WWARN 2015](#)).

Table 4-2 PBPK modeled exposures based on a 5:60 mg (A:L) dose regimen

| | Neonates (≤ 28 days, <5 kg) | Infants (>28 days (1-7 months), <5 kg) |
|--------------------------------------|-------------------------------------|---|
| Artemether (5 mg) | | |
| First dose C_{max} (ng/mL) | 234 | 78.5 |
| Lumefantrine (60 mg) | | |
| Full regimen C_{max} (μ g/mL) | 5.1 | 5.4 |
| C_{168h} (ng/mL)* | 530 | 270 |

Based on PBPK simulations, with an individual artemether dose of 10 mg, C_{max} in infants <5 kg BW is expected to be in the range of the C_{max} observed in infants ≥ 5 kg BW, but at the high end. Because of the neurotoxicity risk, an individual artemether dose of 5 mg was selected in order to remain conservative. This dose is expected to provide a C_{max} that is still efficacious but at least two fold lower than the highest exposures observed in infants/children ≥ 5 kg BW. C_{max} , not AUC, was targeted because only two data points around C_{max} can be captured in this population, due to limitation in blood draws. Due to the same limitation, a reliable estimate of AUC could not be established in study B2306 (COA566B2306). For lumefantrine, a 60 mg individual dose was selected which would provide a total exposure within the observed safe exposures. This dose is expected to provide a $C_{max}>10$ fold of an effective concentration of 200 ng/mL if patients are well fed.

This leads to doses of 5 mg and 60 mg (ratio 1:12) respectively for artemether and lumefantrine that will be assessed in the present study. The ratio is therefore different from the 1:6 ratio (artemether:lumefantrine 20 mg:120 mg dispersible tablet) used in the rest of the population (≥ 5 kg BW), but it is not expected to adversely impact treatment outcome. The confidence in the prediction is moderate as the physiology affecting the exposure to these two compounds is not fully known and variability does exist, especially in the youngest patients (Cohort 2, ≤ 28 days). As a consequence, in order to minimize the risk, an early exposure check will be performed in a staggered fashion:

- in the first 9 patients in Cohort 1 (>28 days) where the risk is lower
- in Cohort 2, in the first 3 patients in the highest age subgroup (15-28 days, Cohort 2.1), and only then in the lower two age subgroups (1-7 and 8-14 days, Cohort 2.2), to further decrease the risk
- in the first 9 patients in Cohort 2 (1-28 days subgroup, Cohort 2.1 and 2.2), once the step directly above has been completed
- in case exposure data in the 1-28 day subgroup in the step right above is not sufficient to inform about the optimal dose for this population, an additional PK check may be performed after 9 patients of the 15-28 day subgroup have been recruited at the same dose across Cohort 2.1 and 2.2 (additional patients will then be recruited in Cohort 2.2 to this effect)

The dose used in Cohort 1 and in the highest age subgroup in Cohort 2 may be modified as required, either upwards or downwards before including further patients. In the event the dose deemed suitable in the highest age subgroup in Cohort 2 is not suitable for either or both lower age subgroups in Cohort 2, recruitment will be stopped and no further doses will be evaluated in the concerned subgroup(s). If no dose at all can be determined as suitable in Cohort 2, the cohort will be stopped.

The PBPK model will be updated and qualified periodically with the available PK data from Cohort 1 and/or Cohort 2 and PBPK simulations may be used to support the recommendation of an appropriate dose for this population.

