12.8.2 Secondary endpoint(s)

Power consideration for Day 8 (168 h) lumefantrine concentration

The Day 8 (168 h) lumefantrine concentration is the key secondary endpoint. The distribution of Day 8 lumefantrine concentration is best described by log normal distribution. In Study B2306, the standard deviation for the log concentration from 16 infants was 0.65. Based on the standard deviation of 0.65 in log scale, a sample size of 16 evaluable patients will provide 80% probability that the observed half width of 2-sided 90% CI for the log concentration is ≤ 0.337 or 1.4 times in terms of ratio (nQuery Advisor 8). This sample size is applied to each cohort.

The percentage of patients who are not evaluable for Day 8 lumefantrine concentration may be higher than that for artemether C_{max} which is based on the concentrations on Day 1. Taking into account about 25% of patients not evaluable for this PK analysis, about 22 patients will be enrolled in each cohort in order to achieve the number of patients evaluable for this analysis as specified above.

Power consideration for PK checking in each cohort

After about 9 patients have been enrolled in each cohort, PK checking will be performed to see if the dose level should be adjusted. Considering that about 10% of patients would be non-evaluable for artemether C_{max}, this will lead to about 8 patients evaluable for artemether C_{max}.

The probability that the observed half width of 2-sided 90% CI in log scale is ≤ 0.693 or 2 in terms of ratio for artemether C_{max} is 96% if the standard deviation in log scale is same as the assumed 0.65 or 80% if the standard deviation in log scale is as high as 0.85 (nQuery Advisor 8).

Note:

The requirement for an evaluable number of patients is 16 for both the primary endpoint (artemether C_{max} (max concentration between concentrations at 1 hour and 2 hours)) and the secondary endpoint (Day 8 (168 h) lumefantrine concentration). An additional number of patients is included due to potential dropouts for each endpoint. In case that the number of dropouts is less than expected, the enrollment for a cohort may be stopped after at least 16 patients are deemed evaluable for PK analyses (C_{max} or Day 8 concentration).

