2.6.2 Statistical hypothesis, model, and method of analysis

Ninety percent (90%) 2-sided confidence intervals for the geometric mean will be calculated for Day 8 (168 h) lumefantrine concentration based on the log normal distribution by cohort and treatment group using the PK analysis set.

LUM C_{168h} is considered to be comparable with historical data if the upper limit of 90% confidence interval is not less than the Historical values. The desired historical values are displayed in the Appendix in [Table 5-7](#).

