3.1.2 Secondary endpoint(s)

Power consideration for Day 8 (168 h) lumefantrine concentration

The Day 8 (168 h) lumefantrine concentration is the key secondary endpoint. The distribution of Day 8 lumefantrine concentration is best described by log normal distribution. In Study B2306, the standard deviation for the log concentration from 16 infants was 0.65. Based on the standard deviation of 0.65 in log scale, a sample size of 16 evaluable patients will provide 80% probability that the observed half width of 2-sided 90% CI for the log concentration is ≤ 0.337 or 1.4 times in terms of ratio (nQuery Advisor 8). This sample size is applied to each cohort.

The percentage of patients who are not evaluable for Day 8 lumefantrine concentration may be higher than that for artemether C_{max} which is based on the concentrations on Day 1. Taking into account about 25% of patients not evaluable for this PK analysis, about 22 patients will be enrolled in each cohort in order to achieve the number of patients evaluable for this analysis as specified above.

Power consideration for PK checking in each cohort

After about 9 patients have been enrolled in each cohort, PK checking will be performed to see if the dose level should be adjusted. Considering that about 10% of patients would be non-evaluable for artemether C_{max} , this will lead to about 8 patients evaluable for artemether C_{max} . The probability that the observed half width of 2-sided 90% CI in log scale is ≤ 0.693 or 2 in terms of ratio for artemether C_{max} is 96% if the standard deviation in log scale is same as the assumed 0.65 or 80% if the standard deviation in log scale is as high as 0.85 (nQuery Advisor 8). Additional optional PK checks can also be implemented.

Note:

The requirement for an evaluable number of patients is 16 for both the primary endpoint (artemether C_{max} (max concentration between concentrations at 1 hour and 2 hours)) and the secondary endpoint (Day 8 (168 h) lumefantrine concentration). An additional number of patients is included due to potential dropouts for each endpoint. In case that the number of dropouts is less than expected, the enrollment for a cohort may be stopped after at least 16 patients are deemed evaluable for PK analyses (C_{max} or Day 8 concentration).

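### Protocol 4.2 says Day 8 lumefantrine should be at least 200 ng/mL, but no planned analysis compares the results with 200, and the SAP's criterion can be met by a cohort whose geometric mean is below it

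*Protocol*

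**What the plan says.** Protocol 4.2 lists what was weighed when the doses were chosen. On lumefantrine it says: "Exposure to lumefantrine should also be adequate, especially the Day 8 plasma concentration (which is a surrogate efficacy marker"; and of that concentration, "it should be ≥ 200 ng/mL on" Day 8, for long-term parasite clearance. The level also matters after dose selection. Protocol 3 opens its rule on extra recruitment with "In the event of inadequate exposure ([Section 4.2](#)), determined at predefined PK checkpoints", and Protocol 6.1.3 makes the same reference for re-runs in Cohort 2.

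Day 8 lumefantrine is the key secondary endpoint. SAP 2.6.2 says: "Ninety percent (90%) 2-sided confidence intervals for the geometric mean will be calculated for Day 8 (168 h) lumefantrine concentration". It calls the result comparable if the upper 90% limit is not below the historical values. Protocol 12.5.3 has a different rule: the interval must contain the historical value. For the PK checks, 12.5.3 includes Day 8 lumefantrine in the data reviewed but gives no numerical rule for it.

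The descriptive output (Protocol 12.5.3, SAP 2.9) includes subject listings, arithmetic and geometric means, SD, CV, median, minimum and maximum. The 200 ng/mL level appears neither in Protocol section 12 nor anywhere in the SAP.

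**The concern.** The protocol gives a number for adequate Day 8 exposure, and the analysis judges the endpoint against different numbers. A historical geometric mean answers whether these infants resemble the children studied before. It does not answer whether the cohort, or what share of it, reaches the level the protocol links to parasite clearance. The two answers can differ, because the B2303 geometric mean for 5 to <15 kg (212 ng/mL, SAP Table 5-6) is only just above 200, and the SAP rule lets a cohort fall some way below it.

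At stake is the interpretation of the key secondary endpoint. A report could correctly call lumefantrine comparable with history and say nothing about whether the protocol's own level was reached.

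**Working it through.** **Inputs**
- Level: 200 ng/mL (Protocol 4.2).
- Distribution: "The distribution of Day 8 lumefantrine concentration is best described by log normal distribution" (Protocol 12.8.2).
- Between-patient SD on the log scale: "the standard deviation for the log concentration from 16 infants was 0.65" (Protocol 12.8.2; 0.654 in Table 12-1).
- Model-predicted C168h at 5:60 mg: 270 ng/mL in infants over 28 days and 530 in neonates (Protocol Table 4-2). The text does not say whether these are geometric means.
- Historical geometric means: 212 (B2303, 5 to <15 kg, n = 27), 388 (B2303, 15 to <25 kg, n = 4) and 666 (B2306, n = 16), from SAP Table 5-6.
- Evaluable patients: 16 per cohort.

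**The plan's own figure.** The probability that t(0.95; n−1) × s/√n is at most 0.337, with true SD 0.65, is 86% at n = 16, or 85% conditional on the interval covering the mean. The smallest n reaching 80% is 15 on the first definition and 16 on the second. Allowing for 25% not evaluable, 16/0.75 = 21.3, so 22. The plan's 16 and 22 reproduce; the 80% is a target met, not the value attained.

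**Share below 200.** P(C < 200) = Φ(ln(200/GM)/SD).

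| Geometric mean (ng/mL) | ln(200/GM)/0.65 | Below 200, SD 0.65 | SD 0.50 | SD 0.85 |
|---|---|---|---|---|
| 212 | −0.090 | 46% | 45% | 47% |
| 270 | −0.462 | 32% | 27% | 36% |
| 530 | −1.499 | 7% | 3% | 13% |

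The 0.85 column borrows the protocol's high case for artemether Cmax. The 0.50 column is a low value assumed for range. Neither is a Day 8 figure. If 270 is an arithmetic mean, the geometric mean is 270 × exp(−0.65²/2) = 219 and about 45% are below 200. On the same reading, 530 gives about 12%.

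Another route starts from the value observed in infants under 5 kg. B2306 gave 666 at 120 mg per dose. If exposure were proportional to dose (an assumption), 60 mg gives 333 and Φ(ln(200/333)/0.65) = 22%.

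**What the SAP rule accepts.** At n = 16 with observed SD 0.65, the half-width is 1.753 × 0.65/4 = 0.285. The lowest geometric mean whose upper limit reaches the historical value H is H × exp(−0.285) = 0.752 H.

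| Historical value | Lowest geometric mean that passes | Share below 200 |
|---|---|---|
| 212 | 159 | 64% |
| 388 | 292 | 28% |
| 666 | 501 | 8% |

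Against 212, a simulation of 200,000 cohorts of 16 gives a 90% chance of passing when the true geometric mean is 200 (50% below 200), and a 50% chance when it is 160 (63% below).

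**What the protocol rule accepts.** The interval contains 212 when the observed geometric mean lies between 159 and 212 × exp(0.285) = 282. Across that range, 64% down to 30% of patients are below 200.

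**Precision of a proportion.** 11 of 16 is 69% (Clopper-Pearson 95% interval 41% to 89%). With about 8 evaluable patients at a PK check, 6 of 8 is 75% (35% to 97%).

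**The case against.** A reader might infer that 200 ng/mL is a responder threshold for each child and that the plan ignores it. The documents do not settle that. Section 4.2 presents the figure as a dose-selection consideration and does not say whether every child, a given share or a typical child should reach it. What remains is that, on either reading, no planned analysis compares the results with 200.

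A reader might also infer that low values would go unseen. They would not. Listings, minimum and median are planned, the median shows whether at least half of patients reach 200, and the DMC reviews PK with safety and efficacy. The outcome that the marker stands for is also measured directly, through PCR-corrected ACPR at Days 15, 29 and 43 and recrudescence incidence. This limits the harm. But Day 29 ACPR is not available when the checks are made on Day 15 data, and nothing planned states the share at or above 200.

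Third, the size depends on the comparator. SAP 2.6.2 does not name a row of the historical table. Against 666 the lowest passing geometric mean is 501, and the problem largely disappears. The 212 row is assumed here because both documents single out that weight group for the primary endpoint.

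Fourth, by the same arithmetic nearly half of the B2303 reference children would have been below 200, although the protocol treats previous exposures in children of at least 5 kg as safe and efficacious. So a sizeable share below 200 does not by itself show that a dose is inadequate. That stands, and no such claim is made here.

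Lastly, the interval at n = 16 is wide. That is true, but the plan already reports Clopper-Pearson intervals for ACPR in cohorts of this size.

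**Conclusion.** The concern holds as a mismatch between the level named in Protocol 4.2 and the criterion in Protocol 12.5.3 and SAP 2.6.2. About 32% to 46% of infants over 28 days would be below 200 ng/mL at geometric means of 270 to 212, while the SAP rule against 212 can be met at about 159, itself below 200, with about 64% below. These shares should not be carried over to the whole study: at the neonatal prediction the figure is about 7%.

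The result assumes that the B2306 log SD of 0.65 carries over, that 270 and 530 are geometric means, and that 212 is the comparator. The SD could be larger: if the 386 in Protocol Table 4-1 is an arithmetic mean from the same B2303 children as the 212, the implied log SD is √(2 ln(386/212)) = 1.09, which gives 48% below 200 at 212.

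The correction is a cheap improvement to how the endpoint is reported. Nothing here shows that the dose under study is inadequate.

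**What to change.** 1. State in Protocol 4.2 and SAP 2.6.2 whether 200 ng/mL applies to each patient or to a typical value, and reconcile the two sections. At the same time, name the comparator row, correct the pointer from Table 5-7 to Table 5-6 (where the reference values are), and resolve the difference between the protocol's containment rule and the SAP's upper-limit rule, since SAP section 4 declares no change from the protocol.
2. In SAP 2.6.2, add the number and percentage of patients with C168h of at least 200 ng/mL, by cohort and dose level, with a Clopper-Pearson 95% interval.
3. Report the geometric mean and its 90% interval against 200 as well as against the historical value.
4. Show items 2 and 3 to the DMC at the PK checks and interim assessments as description only, without a new dose-decision rule. A cross-tabulation with PCR-corrected ACPR is optional; both documents already warn that PK/PD work at this sample size is of limited value.

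The cost is one table from data already collected. The downside is a wide interval and possibly a less favourable reading of lumefantrine exposure.
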